Serum biomarker measurements will be performed: until disease progression is documented (every 12 weeks +/- 1 week).

All subjects who discontinue treatment before disease progression (eg, due to unacceptable toxicities) will be followed for PFS (eg, radiographic tumor evaluations) every 12 weeks until progression of the disease or the end of the study (unless the reason for abandoning the study is the total withdrawal of consent).

Once the patient has progressed, the long-term follow-up period of 24 months will begin from the date of progression (every 3 months).

Single-arm, multicenter, prospective phase II clinical trial for biomarker validation in patients with advanced and / or metastatic colorectal cancer with non-mutated KRAS gene treated with chemotherapy plus biweekly cetuximab as first-line therapy

K-RAS, in patients who do not have a previous determination, and other markers of tumor tissue will be measured at the University Clinic of Navarra (CUN) and the markers of the blood samples will be measured at the Hospital Clínic de Barcelona (HCB) .

Biomarkers will be measured prior to patient enrollment. In addition, blood samples will be collected every 3 months until disease progression.

The proposed biomarkers (BRAF, MMP7 / IGF-1RP / MMP-7 (DP), PIK3CA-PTEN) will be used as independent variables in a multivariate model containing other established prognostic variables to predict PFS. A classification will be constructed based on the ability to predict the response of the biomarkers.

5.1.1 Premature withdrawal of treatment:

Treatment will be interrupted in case of:

Withdrawal of consent from the patient

[figure not shown]
Progressive disease

Intolerable toxicity

Investigator's decision based on what he considers best for the patient

Single-arm, multicenter, prospective phase II clinical trial for biomarker validation in patients with advanced and / or metastatic colorectal cancer with non-mutated KRAS gene treated with chemotherapy plus biweekly cetuximab as first-line therapy

Study Schema

a Day 1 = day of the first treatment administration.

b Subjects' tumor response will be assessed every 12 weeks, throughout the trial until PE (per revised RECIST 1.1 criteria) or withdrawal from the study.

c Subsequent cycles could be delayed due to toxicities associated with cetuximab or chemotherapy.

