10.2. Study variables, subgroups and covariates

10.2.1 Principal endpoint

The primary endpoint is progression-free survival comparing two cohorts, which will be defined according to the classification based on the predictive ability of biomarkers to respond.

Progression-free survival time (PFS): time from the date of inclusion to the date of radiological progression or death (whichever occurs first). Subjects who have not exhibited progression while in the study and have not died while in the study will be censored on the last radiological evaluation date with no evidence of progression. Subjects who have completed study treatment before 48 weeks for any reason should be followed up every 12 weeks as described in this protocol. Subjects who have undergone surgery for metastases will not be censored on the date of surgery, but will be followed as described in the study every 12 weeks until progression is documented. Subjects receiving second-line treatment without documented disease progression will be censored on the date of the last radiological evaluation without progression prior to the change in treatment. If for any reason only the baseline CT was performed (resignation of the subject to continue in the study or loss of follow-up), the case will be censored on day +1 of the inclusion date.

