10.2.5 Considerations about the sample size

Two groups will be defined based on the classification constructed from the clinical variables and the proposed biomarkers.

The Log-rank method has been used instead of a binomial method for the sample calculation in order to include all the events that occur during follow-up.

A minimum difference of 20% (60 vs. 40%) in PFS is expected at 12 months between groups and with the following assumptions:

Alpha error (bilateral): 5%

Beta error: 20%

Monthly recruitment: 8 patients

Percentage of patients with classification = 0 is 40%

The number of patients required is 155 patients to be recruited in 24 months and a total duration of the trial (recruitment + follow-up) of 28 months for 115 events to occur.

Assuming 10% non-evaluable pts we should include a total of 170 pts.

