10.4 Analysis of the main variables of the study

The Cox regression analysis will be performed with the experimental biomarkers and the following prognostic variables (LDH, functional status, age, limited resectable disease (<3 nodules and <5cm). A classification will be performed using the most discriminatory variables. The classification It will be carried out with all the clinical variables of impact in the univariate analysis, including the 4 clinical variables (LDH, functional status, age, limited resectable disease (<3 nodules and <5 cm) and the 3 pathways previously described (BRAF, DP and PTEN). -PI3K) The classification will be carried out with the variables with the greatest impact in the multivariate analysis.

The proposed sample size ensures the construction of a consistent multivariate analysis.

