6.5.1.5. Analysis of main study variables

The primary efficacy analysis of this trial was performed based on all subjects who provided their informed consents, were included in the trial, and did not present significant protocol deviations throughout the study period. .

Continuous and ordinal variables between independent groups were compared using the Wilcoxon rank-sum test and proportions were compared with Fisher's exact test. Clinical endpoints were ORR, DoR, PFS, and OS. Tumour assessments by CT scans were performed every 3 months until PD. Patients without a second CT scan evaluation were not assessable for ORR.

PFS was defined as the time of the signature of the ICF date until PD or death from any cause. Patients who did not experience PD or death were censored on the date of last examination. For more information regarding censoring see in Section 7.5.1.1. OS was defined as the time from the signature of the ICF date to death from any cause. Patients lost to follow-up or still in the study at database closure have been censored at the date last known to be alive.

Survival analyses including PFS and OS were performed using Kaplan–Meier methods. Cox proportional hazards regression with the Efron method for ties was used to identify prognostic factors for PFS and OS.

Multivariable analysis was performed using subject-matter knowledge and deciding a *priori* the variables to adjust by age (>65 years), sex, tumour site (right vs left), surgery of primary tumour, liver only metastases (<3 nodules and <5 cm vs >3 nodules or >5 cm), ECOG PS, LDH (>450 U/L) and CEA, BRAF mutational status, and type of therapy. This analysis was later adjusted by variables with p-values <0.10 in the

univariate analysis via the automated stepwise selection of variables (p-value for variable entry into the model was 0.2 and p-value to keep the variable in the model was 0.1).. All p-values were two sided.

The proposed sample size ensures establishing a consistent multivariable analysis. Clinical variables and biomarkers were used to build scores intended to predict 12- months PFS as following:

1. A multivariable Cox model was built with those clinical variables that in the univariate analysis had a p-value ≤ 0.15 (PS, chemo regimen, sidedness, resectable liver metastases).

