2. A score was established for each patient by adding up the regression coefficients of the multivariable Cox model present in these patients. If for example PS>0 was a negative predictor for PFS (i.e. regression coefficient is negative; e.g. -0.5) and left side tumour was a positive prognostic factor (regression coefficient was positive, e.g. 0.6) then for a patient with PS>0 and left sided tumour the two scores were added (-0.5 + 0.6=0.1). If a patients has PS=0 then the score to be added is 0, as it is the case for right sided tumour in the example.
3. Using a logistic regression model for the outcome 12-months PFS, a ROC curve was computed to choose the score cut point that classifies most patients correctly 4. Patients were dichotomized according to that cut point.
5. Steps 2 to 4 were repeated, adding each of the three biomarkers.
6. Definition of the discriminating power of the 4 scores for prognosis of or 12-months PFS according to these results were compared via ROC curves.
7. Determination of the most suitable score for 12-months PFS according to these results.

The four scores included in the first multivariate model using clinical factors where PS>0, chemotherapy with FOLFIRI and cetuximab, left sided and resectable liver metastases were considered (Score 1). The additional scores considered the four clinical factors above plus the status of each biomarkers (Score 2: BRAF mutation; Score 3: PI3K mutant or PTEN ≤ 3) and Score 4: Double-positive Phenotype (DP).

All analyses were performed using SAS V9.3 (SAS Institute, Cary, NC, USA) statistical software.

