6.5.2. DETERMINATION OF SAMPLE SIZE

It was the aim of the study to identify two groups based on the well-established categories of clinical variables and the proposed biomarkers which are prognostic regarding PFS. The sample size should be sufficient detect a clinically relevant difference in PFS with a log-rank test between the two groups, given the following assumptions:

- The difference in PFS at 12 months between the two groups is at least 20% (i.e. 50% vs 30%) corresponding to a hazard ration of 1.79 assuming an exponential distribution. • Alpha error (two-tailed): 5%
- Beta error: 20%
- Monthly recruitment: 8 patients
- Percentage of patients with classification= 0: 40%

Initially, the number of patients required to be recruited in 24 months was 155 for 115 events to occur. Assuming a 10% proportion of potentially non-assessable patients, a total of 170 patients were needed to be included. After recruiting 157 patients, it was determined that about 70 of these patients had insufficient samples for biomarker analysis preventing their inclusion into the analysis of the primary objective. Therefore, in order to observe the 115 events necessary to evaluate the primary endpoint, the total number of patients was increased up to 221 recruited in 47 months (4–5 patients per month). Finally, the total study duration was 70 months (recruitment + follow-up).

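### The SAP never enters BRAF, DP and PI3K-PTEN as joint candidates in one model or score, so the two-group comparison that the trial was sized for is not among its analysis steps

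*SAP*

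**What the plan says.** **Protocol.** Section 5.1 says the three proposed biomarkers "will be used as independent variables in a multivariate model containing other established prognostic variables to predict PFS". Section 10.4 names seven candidates for the Cox analysis: LDH, functional status, age, limited resectable disease, and the BRAF, DP and PTEN-PI3K pathways. It continues: "The classification will be carried out with the variables with the greatest impact in the multivariate analysis". The primary endpoint in 10.2.1 is "progression-free survival comparing two cohorts, which will be defined according to the classification based on the predictive ability of biomarkers to respond", and the sample-size section (10.2.5) states: "Two groups will be defined based on the classification constructed from the clinical variables and the proposed biomarkers".

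**SAP, analysis steps.** In 6.5.1.5 a clinical score is built from Cox coefficients and dichotomised at a ROC cut point. Step 5 then reads "Steps 2 to 4 were repeated, adding each of the three biomarkers". The same section settles what this means: "The additional scores considered the four clinical factors above plus the status of each biomarkers". Score 2 adds BRAF, Score 3 adds PI3K/PTEN and Score 4 adds DP. Scores A to D in the synopsis follow the same pattern. The primary comparison in 6.5.1.1 sets the AUC of the clinical score against the AUC with each marker added. The a priori multivariable Cox list in 6.5.1.5 ends with "LDH (>450 U/L) and CEA, BRAF mutational status, and type of therapy" and contains neither DP nor PI3K-PTEN.

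**SAP, aim and sizing.** Section 6.5.2 still describes the aim as to "identify two groups based on the well-established categories of clinical variables and the proposed biomarkers which are prognostic regarding PFS", with a log-rank test between those two groups. The statistical methods in the synopsis say the same.

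**The concern.** The protocol describes one model, one classification and one comparison. The SAP describes four scores, none holding more than one biomarker, and compares their 12-month AUCs. It gives no reason for the change, and its own sample-size section still assumes the protocol's design.

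Two things are at stake. First, separate one-marker scores cannot show whether a marker carries information beyond the other two. That is what the protocol's joint model would show. Second, the 115 events and 80% power were derived for a log-rank test between two groups from a combined classification. The analysis steps contain neither that classification nor that test, and the AUC comparison that replaces them has no sample-size basis in the documents.

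**Working it through.** **1. Can step 5 be read as cumulative?** Taken alone, yes: BRAF could be added, then PI3K-PTEN, then DP. The definitions of Scores 2 to 4 in 6.5.1.5 and of Scores A to D in the synopsis rule this out. Each is the clinical factors plus one marker.

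**2. What the 115 events were sized for.** Inputs from Protocol 10.2.5: 12-month PFS 60% vs 40%, two-sided alpha 5%, power 80%, 40% of patients with classification 0. I take these 40% as the low-hazard group and assume exponential PFS.
- HR = ln(0.40)/ln(0.60) = 1.794.
- Freedman's formula with k = 60/40 = 1.5: (1.960 + 0.842)² × (1 + 1.5 × 1.794)² / [1.5 × (1.794 − 1)²] = 113.1. This rounds up to 114, close to the stated 115.
- Schoenfeld's formula for the same split gives 96.

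So the event count belongs to a single 40/60 split. (As a separate matter, the SAP's 50% vs 30% implies HR ln(0.30)/ln(0.50) = 1.737, not the 1.79 it states.)

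**3. How far single-marker splits are from that design.** Counts from SAP Table 6: BRAF mutant 20/181 (11.0%), DP 23/181 (12.7%), PI3K mutant or PTEN ≤3 98/167 (58.7%). Power with 115 events is Φ(√[115·p(1−p)] × ln HR − 1.96), for HR 1.737 to 1.794:

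| Split | Power |
|---|---|
| Planned 40/60 | 83% to 87% |
| BRAF alone | 46% to 50% |
| DP alone | 51% to 55% |
| PI3K/PTEN alone | 83% to 87% |
| Any marker positive vs none (32/68 if the markers are independent) | 79% to 83% |

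These figures describe the markers as two-group splits. They do not describe the dichotomised Scores 2 to 4, whose split depends on the cut point. They show only that the sizing does not carry over to the markers one at a time.

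**4. Is the joint model feasible?** Three markers plus three or four clinical factors give 6 or 7 coefficients: 115/6 = 19.2 and 115/7 = 16.4 events per coefficient. The protocol's seven candidates also give 16.4. All three markers are known in at most 69 + 98 = 167 patients. If 115 events in 181 patients fell proportionally, 115 × 167/181 = 106 events would remain, or 15.2 to 17.7 per coefficient.

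**5. Would joint testing gain power?** This was simulated with 700 trials per scenario, Table 6 prevalences, independent markers, 40% PFS at 12 months, and assumed prevalences for the clinical factors. The comparison is a 3-df likelihood-ratio test of all three markers against at least one significant single-marker test after multiplicity correction.
- All three HRs 1.4, n = 181: about 68% vs 54% to 55%.
- Same effects, n = 167: 64% to 66% vs 50% to 51%.
- One active marker: BRAF HR 1.8, 45% vs 47%; PI3K-PTEN HR 1.5, 57% vs 57%; DP HR 1.8, 53% vs 54%.
- With no marker effect the 3-df test rejected in 4.9% to 6.9% of trials.
- In one run the apparent AUC rose from 0.665 (clinical) to 0.699 (all three markers) with HR 1.4. With no marker effect it still rose from 0.666 to 0.680, so part of such a gain is optimism.

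**The case against.** Several stronger readings are tempting, and the documents do not support them.

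- **That no two markers are ever fitted together.** The Methodology entry in the SAP synopsis reports multivariable analyses of BRAF and PI3K-PTEN with clinical variables. This may be a joint fit of two of the three. It leaves out DP and leads to no score, so only the statement about all three holds.
- **That OS has no classification to use.** Step 4 dichotomises each score and step 7 picks the most suitable one, which could serve for OS. That score can hold at most one biomarker.
- **That the protocol demands a three-marker classification.** Section 10.4 keeps the variables with most impact. All three markers must be candidates, but none has to survive selection, so a one-marker classification could be the protocol's own result. What is missing is the joint candidate model.
- **That the protocol's remark on creating a score (4.4.3) states the purpose for all markers.** It is written about BRAF.
- **That the Cox list in 6.5.1.5 is closed to DP and PI3K-PTEN.** A later stepwise adjustment uses variables with univariate p < 0.10. The covariates listed in 6.5.1.4 are clinical and treatment variables, but the text does not settle whether markers were candidates.
- **That joint testing is generally more powerful.** The gain appears when all three markers have equal effects and vanishes when only one is active. No document supports equal hazard ratios of 1.4.

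It is also fair to say that whether each marker improves on clinical variables is a legitimate question, and the SAP synopsis words the endpoint that way. This stands, but the SAP does not explain the change and contradicts it in 6.5.2.

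**Conclusion.** The point holds in this form: no SAP model or score enters all three biomarkers as joint candidates, and no analysis step compares PFS by log-rank between two groups from a combined classification. This is an unexplained departure from Protocol 5.1, 10.2.5 and 10.4, and an inconsistency with the SAP's own synopsis and 6.5.2. It touches the primary endpoint.

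This conclusion rests on the text and needs no numerical assumption. The size of the consequence is less certain. The single-marker powers in step 3 assume that a marker alone carries the hazard ratio planned for the whole classification. The simulated gain of about 68% vs 55% (64% to 66% vs 50% to 51% at n = 167) applies only to three independent markers with HR 1.4 each. The case for acting is the missing planned analysis, not extra power.

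**What to change.** In SAP 6.5.1.5:

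1. Add one Cox model with the clinical variables and BRAF, DP and PI3K-PTEN as joint candidates, in patients with all three known (at most 167). Report each marker's adjusted hazard ratio with its confidence interval.
2. Apply the selection in Protocol 10.4 to form one two-group classification. Write down the selection rule before fitting, since the protocol gives no threshold.
3. Compare PFS between the two groups by log-rank, as sized in Protocol 10.2.5 and SAP 6.5.2, and use the same groups for OS.
4. Because the groups come from the same data, report optimism-corrected performance by bootstrapping the whole procedure, including selection and cut point.
5. Add DP and PI3K-PTEN next to BRAF in the a priori Cox list.
6. Keep Scores 2 to 4 as secondary.
7. State that the joint analysis restores the protocol's specification and was added after the single-marker AUCs in the synopsis had been seen.

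A 3-df likelihood-ratio test of the three markers may be reported as supportive. Making it primary would replace the planned log-rank comparison with another unplanned test. It also asks whether any marker matters, not what each one adds.

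The cost is SAP wording, one extra model with its bootstrap, and up to 14 fewer patients (181 − 167), or more if missing marker data do not overlap. No new data are needed.

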6.5.2. DETERMINATION OF SAMPLE SIZE

It was the aim of the study to identify two groups based on the well-established categories of clinical variables and the proposed biomarkers which are prognostic regarding PFS. The sample size should be sufficient detect a clinically relevant difference in PFS with a log-rank test between the two groups, given the following assumptions:

- The difference in PFS at 12 months between the two groups is at least 20% (i.e. 50% vs 30%) corresponding to a hazard ration of 1.79 assuming an exponential distribution. • Alpha error (two-tailed): 5%
- Beta error: 20%
- Monthly recruitment: 8 patients
- Percentage of patients with classification= 0: 40%

Initially, the number of patients required to be recruited in 24 months was 155 for 115 events to occur. Assuming a 10% proportion of potentially non-assessable patients, a total of 170 patients were needed to be included. After recruiting 157 patients, it was determined that about 70 of these patients had insufficient samples for biomarker analysis preventing their inclusion into the analysis of the primary objective. Therefore, in order to observe the 115 events necessary to evaluate the primary endpoint, the total number of patients was increased up to 221 recruited in 47 months (4–5 patients per month). Finally, the total study duration was 70 months (recruitment + follow-up).

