Dosage and administration of the investigational product:

FOLFOX6 (m) chemotherapy regimen:

FOLFOX6 (m) chemotherapy will be given on day 1 of each 14-day treatment cycle. FOLFOX6 (m) will be administered at the following doses:

85 mg / m² of oxaliplatin infusion i.v. 120 minutes on day 1 of each cycle.

400 mg / m² leucovorin infusion i.v. 120 minutes on day 1.

One i.v. bolus (2 to 4 minutes) of 400 mg / m² 5-FU on day 1.

5-FU in continuous infusion 2400 mg / m² administered by ambulatory pump over a period of 46-48 hours

FOLFIRI (m):

FOLFIRI (m) chemotherapy will be administered on day 1 of each 14-day treatment cycle. FOLFIRI (m) will be administered at the following doses:

Irinotecan 180 mg / m² in infusion i.v. 120 minutes on day 1 of each cycle.

Leucovorin 200 mg / m², in infusion i.v. 120 minutes on day 1.

One i.v. bolus (2 to 4 minutes) of 400 mg / m² 5-FU on day 1.

5-FU in continuous infusion 2400 mg / m² administered by ambulatory pump over a period of 46-48 hours.

CETUXIMAB:

Administer 500 mg / m² i.v. every 2 weeks.

Single-arm, multicenter, prospective phase II clinical trial for biomarker validation in patients with advanced and / or metastatic colorectal cancer with non-mutated KRAS gene treated with chemotherapy plus biweekly cetuximab as first-line therapy

It is recommended to administer cetuximab first and start with the administration of FOLFOX6 (m) / FOLFIRI (m), at least one hour after cetuximab administration has ended.

Statistical considerations:

Prospective, multicenter, phase II clinical trial designed for the validation of predictive tumor biomarkers in patients with metastatic colorectal cancer and tumor with non-mutated KRAS, treated with chemotherapy and biweekly cetuximab as first-line treatment.

The main objective of this trial is to validate the biomarkers BRAF, IGF1P / MMp7 (DP) and PI3K-PTEN to predict PFS in patients with advanced and / or metastatic colorectal cancer with non-mutated KRAS treated with standard chemotherapy plus biweekly cetuximab as therapy. From first line.

Two groups will be defined based on the classification constructed from the clinical variables and the proposed biomarkers.

A minimum difference of 20% (60 vs. 40%) in PFS is expected at 12 months between groups and with the following assumptions:

Alpha error (bilateral): 5%

Beta error: 20%

The number of patients required is 155 patients. Assuming 10% non-evaluable patients, a total of 170 patients will be included.

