Statistical methods	
Sample size considerations
 
Initially, the number of patients required to be recruited in 24 months was 155 and the total study duration (recruitment + follow-up) was considered to be 28 months for 115 events to occur. After recruiting 157 patients, it was determined that about 70 of these patients had insufficient samples for biomarker analysis preventing their inclusion in the analysis of the primary objective. Therefore, in order to reach the 115 events necessary to evaluate the primary endpoint, the total number of patients to be included in the trial was increased up to 240. Finally, 221 patients were considered sufficient to observe the required number of events. After central reviewing and monitoring, 181 patients with wt-RAS were finally included for efficacy analysis.
 
For sample size calculation, it was assumed that patients could be classified into 2 groups based on their clinical characteristics and their biomarker profile. The log-rank method was planned to be used for the comparison of PFS during follow-up between the two groups. A minimum difference in PFS of 20% (50% vs 30%) was expected between the groups at 12 months, given the following assumptions:
 
 • Alpha error (two-tailed): 5% • Beta error: 20% 
Statistical considerations
 
The primary and the secondary efficacy objectives were analysed using per-protocol analysis. Patients fulfilling all eligibility criteria and with documented wt-RAS status (KRAS and NRAS) were included in the efficacy analysis.
 
Efficacy analysis was based on radiological imaging performed throughout the study and assessed by site investigators. Any finding considered as non-evaluable by the investigator was excluded from the analysis (it was considered as non-existent).
 
For continuous variables, mean, standard error (for efficacy variables), standard deviation (for other measurements), median, 25th percentile, 75th percentile, minimum and maximum, were considered. Categorical variables are presented using frequencies and percentages.
 
The 95% two-sided confidence intervals (CI 95%) of Kaplan–Meier

---------------------	---

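### SAP 6.5.2 pairs 12-month PFS of 50% vs 30% with a hazard ratio of 1.79; those rates give 1.74, and 1.79 belongs to the protocol's 60% vs 40%

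*SAP*

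**What the plan says.** SAP 6.5.2 sizes the trial for a log-rank comparison of two prognostic groups and gives the target as "i.e. 50% vs 30%) corresponding to a hazard ration of 1.79 assuming an exponential distribution". The SAP synopsis repeats the rates without a hazard ratio: "A minimum difference in PFS of 20% (50% vs 30%) was expected between the groups at 12 months". SAP 6.5.2 then ties the sizing to these figures: "Initially, the number of patients required to be recruited in 24 months was 155 for 115 events to occur".

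The protocol uses another pair, both in its synopsis and in 10.2.5: "A minimum difference of 20% (60 vs. 40%) in PFS is expected at 12 months between groups". It gives no hazard ratio. Its sample size is the same: "The number of patients required is 155 patients to be recruited in 24 months", with "a total duration of the trial (recruitment + follow-up) of 28 months for 115 events to occur".

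The other inputs agree between protocol 10.2.5 and SAP 6.5.2: two-sided alpha of 5%, beta of 20%, 8 patients recruited per month, and a 40% share for one class ("Percentage of patients with classification = 0 is 40" per cent in the protocol). Neither document says whether class 0 is the better or the worse group, and neither names an event formula beyond the log-rank method.

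**The concern.** The hazard ratio in SAP 6.5.2 is the only design hazard ratio in either document, and it does not follow from the rates printed beside it. It follows from the protocol's rates. So the SAP's rates point to one design effect and its hazard ratio to the other, while the patient and event numbers stay the same.

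The figure of 115 events matters because SAP 6.5.2 gives it as the reason for enlarging the trial to 221 patients. Someone checking that target needs to know which difference it was set to detect, and with what power.

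**Working it through.** **Inputs.** 12-month PFS of 50/30 (SAP synopsis and 6.5.2) and 60/40 (protocol synopsis and 10.2.5); exponential PFS (SAP 6.5.2); two-sided 5%; 80% power; a 40:60 split; 8 patients per month; 155 patients; 115 events; 24 months of recruitment and 28 months in total (protocol 10.2.5).

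**1. Hazard ratio.** Under an exponential model, HR = ln(S_worse) / ln(S_better).
- 50/30: ln 0.30 / ln 0.50 = 1.737, so 1.74.
- 60/40: ln 0.40 / ln 0.60 = 1.794, so 1.79. This reproduces the printed figure.

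Other readings of 50/30 do not give 1.79: the ratio of medians is 1.737, the odds ratio 2.33, the ratio of PFS rates 1.67 and the ratio of failure rates 1.40.

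**2. Rounding.** With the difference held at 20 points, 49.5/29.5 gives 1.736 and 50.5/30.5 gives 1.738. A 21-point difference, 50.5/29.5, is needed to reach 1.787.

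**3. Which pair fits 155 patients and 115 events?** With uniform accrual over R months and analysis at T = 28, the probability of an event in a group with monthly hazard λ is 1 − [exp(−λ(T−R)) − exp(−λT)] / (λR), where λ = −ln(S)/12. At 8 per month, 155 patients take 155/8 = 19.4 months, not the stated 24, so both lengths are shown. Expected events from 155 patients:

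| Pair | Share in better group | R = 19.4 | R = 24 |
|---|---|---|---|
| 50/30 | 40% | 115.1 | 104.8 |
| 50/30 | 60% | 109.5 | 99.4 |
| 60/40 | 40% | 100.6 | 90.8 |
| 60/40 | 60% | 94.4 | 84.9 |

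For 50/30 with 40% in the better group and R = 19.4, the event probabilities are 0.634 and 0.814. Events are 62 × 0.634 = 39.3 and 93 × 0.814 = 75.7. The standard error of ln HR is √(1/39.3 + 1/75.7) = 0.197, and power is Φ(0.552/0.197 − 1.960) = 80.2%. This one cell reproduces 155 patients, 115 events and 80% power together.

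**4. Events needed from formulas without accrual.** (1.960 + 0.842)² = 7.849.
- Schoenfeld, d = 7.849 / [0.24 (ln HR)²]: 107.3 for 50/30 and 95.8 for 60/40.
- Freedman, d = 7.849 (1 + φHR)² / [φ(HR − 1)²], where φ is the ratio of worse-group to better-group patients. With φ = 1.5 (60% in the worse group): 125.2 and 113.1. With φ = 0.667: 100.9 and 90.1.

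So 60/40 also has a near match to 115, namely 113.1 events by Freedman with 60% in the worse group.

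**5. Power at 115 events.**

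| Formula | 50/30 | 60/40 | Gap (points) |
|---|---|---|---|
| Schoenfeld, Φ(√(115 × 0.24) ln HR − 1.96) | 82.7% | 86.6% | 4.0 |
| Freedman, φ = 1.5 | 76.6% | 80.6% | 4.1 |
| Freedman, φ = 0.667 | 84.9% | 88.6% | 3.7 |

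The Freedman rows use Φ(√(115φ)(HR − 1)/(1 + φHR) − 1.96). Gaps are taken from unrounded values.

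**The case against.** The strongest reply is that 50/30 is probably the true basis and 1.79 only a stray number. The accrual model supports this: 50/30 can reproduce 155, 115 and 80% together, while 60/40 gives 85 to 101 events from 155 patients in 28 months under every combination tried. On that view the protocol's rates are the ones that do not fit, and the SAP needs one number changed. Most of this stands, and it would be too strong to say that the documents leave the pair entirely open. But the match needs accrual of 19.4 months and class 0 to be the better group. With the stated 24 months, 50/30 gives only 99 to 105 events, and 60/40 has its own near match by Freedman. The evidence leans to 50/30 without settling it.

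A second reply is that SAP 6.5.2 asks for a difference of 20 points or more, so rates of 50.5% and 29.5% could sit behind the printed figures and give 1.787. This is possible arithmetically but strained, since it needs a 21-point difference where the SAP's own example shows 20.

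A third reply is that little depends on the number. That is correct. SAP 6.5.2 attributes the enlargement to insufficient samples in about 70 patients, with the 115-event target unchanged, and not to the hazard ratio.

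**Conclusion.** The hazard ratio in SAP 6.5.2 is wrong for the rates beside it: 1.74, not 1.79. That part needs only the exponential model that the SAP itself names. The protocol and SAP also give different rate pairs for the same 155 patients and 115 events without explanation. The accrual inputs favour 50/30, on the assumptions set out above.

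The consequence is minor: about 4 points of power within any one formula.

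Three stronger readings are tempting and not supported.
- A reader might infer that the trial is underpowered. Five of the six combinations at 115 events lie between 80.6% and 88.6%. Only 50/30 by Freedman with 60% in the worse group falls below 80%, at 76.6%, and the documents do not say that this formula was used.
- A reader might take it as established that 1.79 was carried over from the protocol's 60/40. The match is exact to two decimals and the inference natural, but no text says so.
- A reader might think that the primary result is affected. The SAP's primary analysis (6.5.1.1) compares areas under ROC curves and does not use this hazard ratio.

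**What to change.** The sponsor should first check the original sizing calculation for the pair of rates that was used. Then:

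1. If 50/30 is the design basis, change the hazard ratio in SAP 6.5.2 to 1.74. If it is not, restore 60% vs 40% with 1.79 in SAP 6.5.2, and 60% vs 40% in the SAP synopsis.
2. Reconcile the rates between the protocol (synopsis and 10.2.5) and the SAP (synopsis and 6.5.2), giving the date and reason of any change. If 50/30 is confirmed, the protocol's 60/40 needs a correction or an explanatory note.
3. Name the event formula and say which group class 0 is, then state the power that 115 events give for the chosen pair. By Schoenfeld, for example, this is 82.7% for 50/30 or 86.6% for 60/40.

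The cost is one look at the sizing file and a few lines of text. It needs no extra patients, visits or follow-up, and no re-analysis.
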